Exclusion Criteria:	
1. History or presence of clinically significant abnormality as assessed by physical examination, medical history, 12-lead ECG, vital signs, or laboratory values, which in the opinion of the Investigator would jeopardize the safety of the patient or the validity of the study results, including torsades de pointes, any bradyarrhythmias, or uncompensated heart failure.2. Chronic use of prescribed opioids (i.e., >120 days in a 6-month period) up to 6 months prior to Screening or any recreational use of opioids.3. Evidence of clinically significant hepatic or renal impairment, including alanine aminotransferase (ALT) or aspartate aminotransferase (AST) >1.5 x upper limit of normal (ULN), bilirubin >1 x ULN, or endocrine laboratory values (including clinically significant thyroid parameters, i.e., thyroid stimulating hormone [TSH], triiodothyronine [T3], and thyroxine [T4]).4. History or family history of sudden unexplained death or long QT syndrome (measure of the time between the start of the Q wave and the end of the T wave in the heart's electrical cycle).5. An average QTcF \geq450 msec or an average QRS interval \geq120 msec from the 12-lead ECGs performed at Screening.6. History of clinically diagnosed hypotension requiring treatment.7. History or presence of any condition in which an opioid is contraindicated (e.g., significant respiratory depression, acute or severe bronchial asthma or hypercarbia, bronchitis, or has/is suspected of having paralytic ileus).8. No more than 3 prescribed doses of an opioid within the 6 months prior to Screening and no use at all within the last month.9. Use of an antipsychotic, anticonvulsant, or mood stabilizer, regardless of indication, within the 3 months prior to Screening.10. History of allergy or hypersensitivity to methadone or related drugs (e.g., opioids).11. Positive test for hepatitis B or human immunodeficiency virus (HIV). Patients with a positive hepatitis C test may be considered for inclusion with approval from the Medical Monitor.12. Any current and primary psychiatric disorder, as defined as a condition that is the primary focus of distress and/or treatment, other than MDD.13. Any lifetime history of bipolar I or II disorder, any psychotic disorder, post-traumatic stress disorder, borderline personality disorder, antisocial personality disorder, obsessive compulsive disorder, eating disorder, intellectual disability, or pervasive developmental disorder.

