1.2.1 Results from Clinical Study REL-1017-111

Study REL-1017-111 was “A Phase 1 Study to Investigate the Safety, Tolerability, and Pharmacokinetic Profile of Single Ascending Doses of d-Methadone in Healthy Subjects.” It was a double-blind, randomized, placebo-controlled study in sequential arms. Safety and PK for REL-1017 (d-methadone) oral administration were determined in ascending dose arms from 5 mg to 200 mg. Pharmacokinetic parameters were calculated for all dose levels, although some individual results had to be excluded due to emesis or statistical analysis criteria.

Pharmacogenomics analysis was performed for subjects exhibiting either fast or slow metabolism of REL-1017. Overall, there were minimal subjective PD effects of REL-1017 up to 150 mg, as assessed by the Bond-Lader VAS. For additional information, please reference the Investigator's Brochure.

The overall conclusions drawn from Clinical Study REL-1017-111 were:

- The MTD for oral REL-1017 in healthy opiate-naive subjects was determined to be 150 mg.
- The PK analysis revealed high variability of the REL-1017 parameters, including C_{max} , time to maximum observed plasma concentration (T_{max}), area under the plasma concentration-time curve from time zero to infinity (AUC_{0-inf}), apparent terminal elimination half-life ($t_{1/2}$), and apparent clearance/bioavailable fraction absorbed (CL/F).
- Statistical models demonstrated linear proportionality of C_{max} and AUC_{0-inf} versus dose, although the result was not statistically significant.
- In general, there were no specific trends observed for T_{max} or $t_{1/2}$ of REL-1017.
- The subjective PD effects of REL-1017 up to 150 mg were minimal.
- The objective measure of PD effects, pupillometry, showed a dose response with greater pupil constriction in the higher dose groups.
- The single doses of REL-1017 administered in this study appeared to be safe with no indication of respiratory depression or clinically significant QTcF prolongation. In terms of tolerability, nausea and vomiting become potential adverse events (AEs) with higher doses.

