4.3 Exclusion Criteria

Patients will not be considered eligible to participate in this study if any one of the following exclusion criteria is satisfied at Screening:

1. History or presence of clinically significant abnormality as assessed by physical examination, medical history, 12-lead ECG, vital signs, or laboratory values, which in the opinion of the Investigator would jeopardize the safety of the patient or the validity of the study results, including torsades de pointes, any bradyarrhythmias, or uncompensated heart failure.
2. Chronic use of prescribed opioids (i.e., >120 days in a 6-month period) up to 6 months prior to Screening or any recreational use of opioids.
3. Evidence of clinically significant hepatic or renal impairment, including alanine aminotransferase (ALT) or aspartate aminotransferase (AST) >1.5 x upper limit of normal (ULN), bilirubin >1 x ULN, or endocrine laboratory values (including clinically significant thyroid parameters, i.e., thyroid stimulating hormone [TSH], triiodothyronine [T3], and thyroxine [T4]).
4. History or family history of sudden unexplained death or long QT syndrome (measure of the time between the start of the Q wave and the end of the T wave in the heart's electrical cycle).
5. An average QTcF \geq 450 msec or an average QRS interval \geq 120 msec from the 12-lead ECGs performed at Screening.
6. History of clinically diagnosed hypotension requiring treatment.
7. History or presence of any condition in which an opioid is contraindicated (e.g., significant respiratory depression, acute or severe bronchial asthma or hypercarbia, bronchitis, or has/is suspected of having paralytic ileus).
8. No more than 3 prescribed doses of an opioid within the 6 months prior to Screening and no use at all within the last month.
9. Use of an antipsychotic, anticonvulsant, or mood stabilizer, regardless of indication, within the 3 months prior to Screening.

10. History of allergy or hypersensitivity to methadone or related drugs (e.g., opioids).
11. Positive test for hepatitis B or human immunodeficiency virus (HIV). Patients with a positive hepatitis C test may be considered for inclusion with approval from the Medical Monitor.
12. Any current and primary psychiatric disorder, as defined as a condition that is the primary focus of distress and/or treatment, other than MDD.

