13. Any lifetime history of bipolar I or II disorder, any psychotic disorder, post-traumatic stress disorder, borderline personality disorder, antisocial personality disorder, obsessive compulsive disorder, eating disorder, intellectual disability, or pervasive developmental disorder.
14. History in the past 12 months of a primary diagnosis of anxiety disorder or panic disorder not related to the current MDE.
15. Current diagnosis of alcohol or substance use disorder, as defined by DSM-5, at Screening or within the 12 months prior to Screening. Patients with the following diagnoses within the past 12 months, however, may be included at the Investigator's discretion: mild alcohol use disorder, mild cannabis use disorder, and any severity tobacco use disorder.
16. A confirmed positive result on the urine drug/alcohol screen at Screening or Check-in. If the urine drug/alcohol screen is positive at Screening, retesting or rescreening may be scheduled with prior approval from the Medical Monitor.
17. Patients who, in the Investigator's judgment, are at significant risk for suicide. A patient with a Columbia-Suicide Severity Rating Scale (C-SSRS) ideation score of 4 or 5 within the last 6 months or any suicide attempt within the past year must be excluded, as should a patient with an ideation score of 4 or 5 or any suicide attempt at the Check-in or Baseline Visit.
18. Patients with a 20% improvement between Screening and Check-in (Day -1) on the HAM-D-17.
19. Patients who did not safely discontinue medications prohibited in Section 4.4.1.
20. Patients receiving new onset psychotherapy (individual, group, marriage, or family therapy) within 2 months prior to Screening or plans to start at any time during participation in the study.
21. Patients who have received electroconvulsive therapy (ECT), repetitive transcranial magnetic stimulation (rTMS), or vagus nerve stimulation (VNS) or who have participated in a ketamine study within the last 6 months.
22. Patients with any clinically significant neurological, hepatic, renal, metabolic, hematological, immunological, cardiovascular, pulmonary, chronic pain, or gastrointestinal disorder. Medical conditions that are minor or well-controlled may be

permitted if they will not increase the safety risk to the patient or compromise interpretation of the safety or efficacy endpoints.

23. Patients taking fluvoxamine or St. John's Wort.

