Herbal drugs/dietary supplements for depression, anxiety, or insomnia	30 days

PRN = As Needed.

¹ The Medical Monitor should be contacted for any questions regarding the potential for pharmacological interactions with concomitant medications used by patients during the study. These include off-label use of medications for depression.

The use of the following medications is prohibited during the study:

1. Antidepressants other than the approved, stable dose started prior to the study; the maximum allowed dose for paroxetine is 40 mg QD, for fluoxetine is 60 mg QD, and for sertraline is 200 mg QD.
2. Antipsychotics
3. Antiepileptic drugs
4. Benzodiazepines and hypnotics used as needed or above the approved doses
5. Stimulants
6. Opioid analgesics
7. Nutritional supplements and non-prescription based herbal preparations with central nervous system (CNS) effects
8. Barbiturates

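### Exclusion 8 is worded the wrong way round, and Exclusion 16 conflicts with the scheduled benzodiazepines that Section 4.4.1 allows

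*Combined protocol and SAP*

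**What the plan says.** **Opioid history.** The lead-in to Section 4.3 sets the operating rule: "Patients will not be considered eligible to participate in this study if any one of the following exclusion criteria is satisfied". Item 8 of that list is "No more than 3 prescribed doses of an opioid within the 6 months prior to Screening and no use at all" within the last month. The Synopsis carries the same text ("an opioid within the 6 months prior to Screening and no use at all within the last month"), so this is not a slip in one place. Three other rules name opioid use or test for it:

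- Item 2: "Chronic use of prescribed opioids (i.e., >120 days in a 6-month period) up to 6 months prior to Screening", or any recreational use.
- Item 16: "A confirmed positive result on the urine drug/alcohol screen at Screening or Check-in", on a panel that includes opiates.
- Item 19: "Patients who did not safely discontinue medications prohibited in Section 4.4.1", where the Section 4.4.1 list of drugs barred during the study includes "Opioid analgesics".

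**Benzodiazepines.** Section 4.4.1 permits them when they are taken on a schedule, at a stable dose within the label, for at least 30 days before Check-in. Its prohibited list bars only as-needed or above-label use. The urine panel in Section 6.2.5.7 and in footnote f of Table 1 includes benzodiazepines and is run at Screening and at Check-in. Item 16 offers a retest or rescreen after a positive at Screening, with Medical Monitor approval. It gives no exception for a permitted prescription.

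**The concern.** These are two inconsistencies in operative eligibility rules.

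Item 8 states what an acceptable patient looks like, but it sits in a list where meeting the item bars entry. Followed literally, it removes opioid-naive patients, the group in which Phase 1 tolerability was established (Section 1.2.1: "The MTD for oral REL-1017 in healthy opiate-naive subjects was determined to be 150 mg"), and leaves in those with more or more recent opioid use.

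Item 16 is the more consequential because intent does not settle it. A patient can comply with Section 4.4.1 and still be excluded for the drug that section permits. Section 6.1.3 requires a patient who fails any entry criterion to be discontinued as a screen failure, and Section 8.1.5 requires eligibility deviations to be described. With about 10 sites, the same patient could be enrolled at one and turned away at another.

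**Working it through.** The plan gives no figure to reproduce, so the check is one of logic and visit timing.

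**1. Item 8 under the Section 4.3 rule (satisfied means ineligible).** The item is satisfied when there are 3 or fewer prescribed doses in 6 months and no use in the last month.

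| Prescribed doses in 6 months | Use in last month | Within the stated limit? | Item 8 satisfied? | Literal result |
|---|---|---|---|---|
| 0–3 | no | yes | yes | excluded |
| 0–3 | yes | no | no | not excluded by item 8 |
| more than 3 | no | no | no | not excluded by item 8 |
| more than 3 | yes | no | no | not excluded by item 8 |

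The result is reversed in 4 of 4 rows. The opioid-naive patient is in the first row.

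**2. Whether another rule restores the limit.**

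- Item 2 starts only above 120 days of prescribed use in 6 months, or with recreational use.
- Item 16 needs a positive urine test.
- Item 19 with Section 4.4.1 requires prohibited drugs to have been stopped; it contains no dose count. Table 3 does not name opioids. Even if its 90-day line for other psychotropics were stretched to cover them, use between 90 days and 6 months before Screening would have no dose limit.
- Items 1 and 22 turn on clinical judgement or a disorder such as chronic pain, not on doses taken.

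Example: 10 prescribed doses ending 2 months before Screening, with negative urine. This is outside the limit (10 > 3), but item 8 does not exclude it, and neither do items 2, 16 or 19, with opioids not counted under the Table 3 psychotropic line. No rule re-admits the opioid-naive patient.

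**3. Item 16 against Section 4.4.1: timing.**

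- Check-in is Day -1 (Table 1).
- Latest start of a permitted benzodiazepine: Day -1 minus 30 days = Day -31.
- Screening runs from Day -30 to Day -2 (Section 3.2).
- Day -31 precedes Day -30, so a permitted user is on drug at Screening and at Check-in: 2 of 2 urine tests.

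**4. What happens if a test is confirmed positive.** Section 4.4.1 allows the patient and item 16 excludes the patient. The retest clause covers a Screening positive only, and a repeat would not be expected to help while the drug continues. Section 4.4.1 sends questions on these medications to the Medical Monitor but does not say how a positive is to be handled.

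**The case against.** **On item 8.** The intent is obvious and all the limits are stated; only the polarity is wrong. For harm to follow, a site, the Medical Monitor and the external review team would all have to reject every opioid-naive patient. The count of 4 of 4 restates the inversion and is not a number of patients. In the 10-dose example, item 1 or item 22 might apply, and Section 4.4.1 requires medications from the 6 months before Screening to be recorded, so the history would be visible. Most of this stands, and mis-enrolment on a large scale is unlikely. However, external review is described as covering key criteria, without saying that item 8 is among them, and item 8 remains the only source of the 3-dose and last-month limits.

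**On item 16.** A specific permission can reasonably be read alongside a general drugs-of-abuse screen. Section 4.4.3 ties the urine tests to abstinence from recreational drugs, the word confirmed is undefined, and the Medical Monitor is already involved. The group may also be small, since item 14 removes some patients with primary anxiety or panic disorder. Being on drug at both tests does not prove that either is positive, and the retest point rests on an expectation about the assay. These limits are fair. They do not supply an exception. Item 16 is not confined to recreational use, and the same list writes allowances out where they are wanted: hepatitis C in item 11, mild cannabis use disorder in item 15. Item 16 has none.

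**Conclusion.** Both parts hold. Item 8 is inverted in Section 4.3 and in the Synopsis, with the literal result reversed in 4 of 4 cases; its practical weight is modest because the intent is plain. Item 16 and Section 4.4.1 give opposite answers for a permitted benzodiazepine user with a confirmed positive, and that user is on drug at 2 of 2 tests.

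The number of patients affected cannot be estimated, because the documents give neither the frequency of scheduled benzodiazepine use nor the sensitivity of the assay. The conclusion on item 16 assumes that the panel can detect the permitted drug and that a positive explained by a prescription still counts as confirmed, a point on which the text is silent. No endpoint, analysis or sample-size figure changes. The text should be corrected, but nothing here invalidates the trial.

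**What to change.** **Item 8 (Section 4.3 and Synopsis).** Reverse the polarity and leave the figures alone, so that satisfying the item makes the patient ineligible. The connective must change with it: the negation of at most 3 doses and no last-month use is more than 3 doses in 6 months or any use in the last month.

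**Item 16 (Section 4.3 and Synopsis) and Section 6.2.5.7.** Reconcile these with Section 4.4.1 by stating, for Screening and for Check-in separately, what happens when a benzodiazepine-positive result is explained by a documented, permitted scheduled prescription. Which rule prevails is for the sponsor to decide.

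**Cost.** A short amendment: one reworded sentence for item 8 and one added sentence for item 16, each in two places, plus a cross-reference in Section 6.2.5.7. There is no change to the analysis. Enrolment may shift modestly, depending on how the sponsor resolves item 16.

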4.4 Study Restrictions

4.4.1 Prohibited Medications

All patients must have discontinued all prohibited medications prior to the Screening period to meet the protocol requirements. Table 3 provides the required duration of time to discontinuation period for selected prohibited medications. All other prohibited medications should be stopped prior to Check-in at the CRU. Benzodiazepines and non-benzodiazepine sleep aids taken as scheduled medications and at stable doses not higher than that in the FDA-approved label for at least 30 days prior to the Check-in are allowed in the study. Any questions regarding these medications should be directed to the Study Medical Monitor. Initiation of these medications during the study is not allowed.

Any medication taken consistently by the patient for 30 days prior to Screening and that is not a prohibited medication may be continued during the study if appropriately documented and captured in the electronic Case Report Form (eCRF). All medications taken within 6 months prior to Screening must be noted on the eCRF.

The Investigators and their designees are obliged to ensure the well-being of all patients during this study. If medical intervention is required during the study, no medication or treatment will be withheld from a patient; and the Investigator will ensure proper documentation is kept in the eCRF. Due to each subject's clinical condition being unique, there is no specific rescue plan or rescue therapy recommended for subjects. If a subject experiences a clinical condition, the Investigator should use clinical judgment and knowledge of the subject's specific condition to institute the best treatment for that subject.

All medications taken by patients after Screening until the completion of the final Follow-Up Visit or the Early Withdrawal (EW) Visit will be documented as concomitant medications. The reported concomitant medications will be reviewed and evaluated by the Investigator to determine if they affect a patient's eligibility or continued participation in the study.

Table 3 Time from Discontinuation of Prohibited Medications, Supplements, and Other Substances

Prohibited Medications, Supplements, and Other Substances	Time from Discontinuation to Check-In¹
Monoamine oxidase inhibitors (MAOIs)	90 days
Tricyclic antidepressants and atypical antidepressants	90 days
PRN Benzodiazepines	30 days
All other psychotropic medications except for those allowed in the study	90 days
Herbal drugs/dietary supplements for depression, anxiety, or insomnia	30 days

PRN = As Needed.

¹ The Medical Monitor should be contacted for any questions regarding the potential for pharmacological interactions with concomitant medications used by patients during the study. These include off-label use of medications for depression.

The use of the following medications is prohibited during the study:

1. Antidepressants other than the approved, stable dose started prior to the study; the maximum allowed dose for paroxetine is 40 mg QD, for fluoxetine is 60 mg QD, and for sertraline is 200 mg QD.
2. Antipsychotics
3. Antiepileptic drugs
4. Benzodiazepines and hypnotics used as needed or above the approved doses
5. Stimulants
6. Opioid analgesics
7. Nutritional supplements and non-prescription based herbal preparations with central nervous system (CNS) effects
8. Barbiturates

4.4.2 Contraceptive Precautions

For men with female sexual partners of childbearing potential, examples of medically acceptable forms of contraception include vasectomy, or male condom for patients plus an additional method of contraception for their female partners. For vasectomized men, original documents obtained after vasectomy or a note from the family physician is required to confirm sterility. In the absence of such documents, it will be assumed that the patient is of childbearing potential, and the patient will be advised to use the medically acceptable birth control methods.

Men must also abstain from sperm donation from Screening until at least 2 months after the last study drug administration.

Females of child-bearing potential (not surgically sterilized and between menarche and 1 year

post menopause) must agree to use 2 methods of contraception through the end of the study and until at least 2 months after the last study drug administration. Surgical sterilization is defined as removal of the uterus and/or both ovaries. Acceptable forms of contraception for female patients include:

- Intrauterine device (IUD)
- Bilateral tubal ligation, bilateral salpingectomy, or bilateral tubal occlusive procedure
- Hormonal contraceptives (e.g., oral, patch, or injectable)
- A double-barrier protection method (e.g., condom, sponge, or vaginal diaphragm with spermicide cream, foam, or gel)

Women must also abstain from egg donation from Screening until at least 2 months after the last study drug administration.

4.4.3 Dietary and Other Restrictions

During the inpatient period for the study, patients will receive a standard diet. No additional food or beverages may be consumed while patients are staying in the CRU. Meals will be served at specific times after the completion of any scheduled assessments.

Aside from the inclusion and exclusion criteria listed in Section 4.2 and Section 4.3, respectively, the patient must agree to abide by each of the following restrictions for the specified time:

- Patients will be asked to abstain from alcohol for 24 hours prior to Screening, 24 hours prior to Check-in to the CRU, while in the CRU, and 24 hours prior to the Day 14 visit.
- Patients will be required to abstain from recreational drug use throughout the study, from Screening until after the Day 21 Follow-Up telephone call. Abstinence from drug use will be confirmed with urine drug screens at Screening and Check-in, and patients will be reminded to adhere to restrictions throughout the study.
- Dosing will occur in the morning following an overnight fast of at least 8 hours.
- Patients will be required to abstain from blood donation during the study and for 30 days following the last study visit. A copy of the Informed Consent Form (ICF) with the study restrictions will be provided to each patient. Patients will be reminded by phone calls prior to study visits to adhere to study restrictions as described in the ICF.
- Patients will be required to follow the ICF and the clinic code of conduct.

